**Medical University of South Carolina
Protocol**

PI Name: [name].

Study Title: Effect of Cognitive Behavioral Therapy and Transcranial Direct Current Stimulation (tDCS) on Fibromyalgia Patients.

TABLE OF CONTENTS

1. Specific Aims.....	1
2. Background and Significance.....	1
3. Preliminary Studies.....	3
4. Research Design and Methods.....	6
5. Protections of Human Subjects.....	9
6. References/Literature Citations.....	12
7. Facilities Available.....	16

A. SPECIFIC AIMS

Aim: Determine the effects of CBT, anodal tDCS over left DLPFC, and combined CBT+tDCS on clinical pain and functioning among a sample of patients with fibromyalgia

Hypothesis 1a: CBT alone will be associated with significant improvements in pain and functioning

Hypothesis 1b: Anodal tDCS plus CBT will yield significant improvements in pain and functioning that exceed those of CBT alone.

This study will be the first randomized, double-blind, controlled study of tDCS technology as an adjunctive pain management strategy for fibromyalgia pain. Data from this trial will likely yield information regarding the feasibility and efficacy of tDCS+CBT as a chronic pain-management approach.

B. BACKGROUND AND SIGNIFICANCE

FIBROMYALGIA (FM): Fibromyalgia is considered to be a multifactorial disorder resulting from the interaction of both genetic and environmental factors, which contribute to its occurrence and expression³. Symptoms of Fibromyalgia include widespread muscle pain, fatigue, disruption in sleep patterns, loss of memory, and mood disorders. Fibromyalgia is commonly associated with other medical conditions such as depression, rheumatoid arthritis, and other stress-related disorders such as posttraumatic stress disorder. The cause of fibromyalgia is unknown; the most prevalent theory being that those suffering from the disease have a lower threshold for pain due to an increased reactivity of pain sensitive nerve cells. The pain and physical debility of this disease produce changes in nearly every area of life. The prevailing medical treatments are aimed at suppression of symptoms, analgesia, and prevention of damage to joints, but these treatments can have adverse side-effects. Therefore, several non-pharmacological pain management techniques have emerged²⁻⁸.

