Passard et al⁹⁵, hypothesized that rTMS of the motor cortex might reduce chronic widespread pain in patients with fibromyalgia. They employed a randomized, double blind, sham-controlled parallel group study analyzing the analgesic effects of repeated daily sessions of unilateral rTMS in 30 patients with widespread pain, quality of life, mood, and anxiety problems due to fibromyalgia. Tender point pain threshold was a secondary outcome. Each treatment session employed a stimulation frequency of 10 Hz and 80% resting motor threshold intensity, resulting in a total of 2000 pulses per session. The primary outcome measure was self-reported average pain intensity over the prior 24 hours using an 11-point numerical scale. Average pain intensity was reported for 1 week as a baseline, during treatment (days 1-14) and until the first follow-up visit to make it possible to determine the onset of treatment effects, then was assessed at each follow-up visit on days 15, 30, and 60. Four patients (two per treatment group) withdrew from the trial between days 30 and 60. Pain intensity was similar in the two groups at baseline and rTMS had a significant effect on average pain intensity scores between baseline and day-15 in comparison with sham stimulation. This effect was not maintained on days 30 and 60. Average pain intensity was significantly lower in the active rTMS group than in the sham stimulation from day 5 to day 14. On day 15, McGill Pain Questionnaire total score and the sensory and affective subscores were significantly lower in the active rTMS group than in the sham-stimulation group. The difference in affective subscore persisted until day 30, whereas the sensory subscore did not. Subjective global pain relief over the last week was significantly greater in the active than in the sham-stimulation group up to day 30. Mean depression and anxiety scores were similar in the two treatment groups at baseline and were not significantly changed by active or sham stimulation. rTMS had no significant effect on the number of tender points. This study showed that rTMS of the primary motor cortex induced a long-lasting decrease in pain and improved quality of life in patients with fibromyalgia, without affecting mood or anxiety levels. One limitation of this study is the design of the sham system.

Table 1. Overview of current TMS fibromyalgia literature including the pilot study recently completed by the Investigators (Short et al)

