Study	Sample Size	Cortical Target	Frequency	Intensity	Pulses Per Session	Sham System	Blind	Concurrent Meds
Sampson et al	4	Right Dorsolateral Prefrontal Cortex	1 Hz	110% rMT	1600	Did not control for Scalp Sensations	Treater was not blind	Permitted
Carretero et al	26	Right Dorsolateral Prefrontal Cortex	1 Hz	110% rMT	1200	Did not control for Scalp Sensations	Single-Blind	Permitted
Passard et al	30	Motor Cortex	10 Hz	80% rMT	2000	Did not control for Scalp Sensations	Double-Blind	Permitted
Short et al	20	Left Dorsolateral Prefrontal Cortex	10 Hz	120% rMT	4000	Controlled for Scalp Sensations	Single-Blind	Permitted

Per description, it makes similar sounds as active rTMS, however there is no form of superficial stimulation to the scalp, which can be problematic as otherwise the active and sham treatments are easily discerned.

There is evidence in the TMS-literature to suggest that slow (1 Hz) right prefrontal TMS has anti-depressant effects as does fast (10 Hz) left prefrontal TMS, however fast left prefrontal TMS appears to have larger effects that benefit more patients with depression than slow right. Following from these findings as well as several pilot studies conducted by our group showing analgesic benefits of fast left TMS in laboratory pain models⁹⁷, chronic neuropathic pain⁹⁸, and post-surgical pain⁹⁹⁻¹⁰¹, we recently completed a preliminary single-blind, sham-controlled trial of fast left dorsolateral prefrontal

rTMS among a cohort of 20 patients with fibromyalgia. Findings suggest significant, long-lasting benefits of real rTMS compared to sham on FIQ scores, average daily pain, and tender points (see Innovation section for a full description of this pilot study).

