PARTICIPANTS: Participants will be 72 patients meeting the American College of Rheumatology (ACR) criteria from diagnosis of fibromyalgia for at least 1-year. Patients must not have any chronic pain conditions other than fibromyalgia, and must not be on chronic opioid therapy for pain. Patients with a history of seizures, who are or might be pregnant, or with metal/electronic implants or devices above the waist will be excluded to ensure tDCS safety. Patients with moderate to severe depression (HRDS>18) at the time of randomization will be excluded, however patients with no depression or only mild depression (HRDS<19) will be eligible provided that the onset of the first depressive episode was after the onset of fibromyalgia (as is commonly seen in patients with chronic pain) in order to exclude patients for whom chronic widespread pain might be a somatic manifestation of the depressive illness. To be eligible for enrollment, BAI scores must be <16 to limit the sample to patients with minimal to no clinical anxiety problems.

tDCS METHODS: tDCS will be delivered in 30-minute-sessions and will be conducted with the Phoresor-II Auto (Model PM850) using 2mA current. This constant current device ramps up to the desired amplitude to minimize discomfort for participants and ramps the amplitude back to 0mA at the end of the session. Electrodes will be standard small (4cm X 4cm) sponge electrodes soaked in a sterile solution of 0.9% sodium chloride insulated by a latex casing. The current density and total charge delivered by the above parameters is consistent with those used safely in the current research literature on tDCS. In all tDCS conditions, participants will undergo anodal stimulation of the left DLPFC (Brodmann Area 9; BA9) and cathodal stimulation of the right DLPFC (which is consistent with the majority of published prefrontal tDCS studies for pain to date) during each of the 6 CBT sessions. The electrodes will be fastened with Velcro strap(s). Specially designed software (by the Investigator) interfaces with an ONTRAK ADU218 Solid State Relay I/O interface connected to the tDCS device permitting normal and reverse current flow between the electrodes in a manner that is completely masked. The software reads the assigned condition directly from an encrypted subject-randomization-file and delivers anodal, cathodal or sham stimulation in a blinded fashion.

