THE BECK DEPRESSION INVENTORY (BDI) is a well-researched, brief self-report depression-screening instrument. This instrument will be used for screening purposes in the laboratory study and to characterize depression in the clinical cohort. The BDI scale assesses suicidal ideation, those patients exhibiting suicidal ideations will be referenced to a therapist in order to further manage their depressive symptoms.

THE BECK ANXIETY INVENTORY (BAI) is a well-researched, brief self-report anxiety-screening instrument. It assesses different aspects of anxiety experience (e.g., physiological, cognitive, behavioral).

THE BRIEF PAIN INVENTORY (BPI) is a self-report questionnaire designed to assess pain intensity and the impact of pain on general functioning, relationships and mood.

DAILY PAIN/MOOD DIARIES will be administered via paper and pencil to patients in the clinical pilot Diaries will assess daily (via VAS) average pain, pain at its worst, pain unpleasantness, mood, activity level, and will capture hours of sleep and sleep quality ratings.

THE MCGILL PAIN QUESTIONNAIRE (MPQ) is a self-report scale designed to capture the quality and intensity of pain experience. The ratings load onto 4 factors: 1) Sensory, 2) Affective, 3) Evaluative, and 4) Miscellaneous.

THE MOS SHORT-FORM12 HEALTH SURVERY (SF12) will be used to assess quality of life across the eight QOL domains captured with the measure during the trial.

THE FIBROMYALGIA IMPACT QUESTIONNAIRE will be used to assess pain symptoms and functioning specific to FM.

PROCEDURES:

Clinical Pilot Trial: Patients will be recruited by fliers or referred by providers in the Chronic Pain Clinic, Dept. of Rheumatology and the Behavioral Medicine Clinic at MUSC. Participants will be screened on the telephone, consented, oriented to the study, and instructed in the use of pain diaries. After a 2-week baseline phase, patients will undergo QST. They will then start the manualized CBT intervention in the Behavioral Medicine Clinic at MUSC with simultaneous tDCS (real or sham; randomized and masked). Participants will undergo 1 session per week for 6 weeks. After the last session, participants will undergo another QST session. Patients will continue to complete the pain diaries throughout the treatment as well as a 4-week follow-up phase. At 3 and 6 months, participants will return to the lab to re-complete the dependent measure battery.

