DATA ANALYSIS PLAN AND POWER: Hierarchical Linear Modeling (HLM) will be used to examine changes in pain, sleep and activity over time while controlling for mood (time-series), and controlling for

baseline depression, anxiety and pain scores as a function of group (active vs sham tDCS). HLM will also be used to examine changes in quality of life and functional impairment due to pain. Previous research on the effects of CBT for pain and of tDCS for pain suggests that each is associated with a medium effect-size. To be conservative, assuming that there is no synergistic interaction-effect of combined tDCS and CBT, power is good to detect a group-level main effect ($1-\beta>.80$) with as few as 18 subjects per group. If the interaction-effect is large, as is expected, power is excellent to detect main and interaction effects ($1-\beta>.90$).

E. PROTECTION OF HUMAN SUBJECTS

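### The only model for pain, sleep and activity adjusts for mood recorded during treatment, so it misses the total tDCS effect if mood differs between arms

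*Combined protocol and SAP*

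**What the plan says.** The Data Analysis Plan and Power paragraph (section D) describes one HLM for these outcomes. It will "examine changes in pain, sleep and activity over time while controlling for mood (time-series". Baseline depression, anxiety and pain are named separately as further covariates, and the group contrast is active against sham tDCS. Because the baseline terms are listed apart, the mood term cannot mean baseline mood alone. Lag and centring are not stated, and no reason is given for the adjustment.

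The only measure described as recording mood daily is the diary (Dependent Measures), whose items cover "average pain, pain at its worst, pain unpleasantness, mood, activity level, and will capture hours of sleep". Diaries begin in a 2-week baseline phase (Procedures). After that, "Patients will continue to complete the pain diaries throughout the treatment as well as a 4-week follow-up phase".

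Hypothesis 1b (Specific Aims) reads "Anodal tDCS plus CBT will yield significant improvements in pain and functioning that exceed those of CBT alone". No hypothesis concerns pain relief at a fixed level of mood, and no other model is described for pain, sleep or activity. The HLM for quality of life and functional impairment names no mood adjustment and is not part of this point.

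**The concern.** Randomisation balances what exists before treatment. Mood recorded afterwards can itself be changed by treatment, and holding it fixed then changes the question being answered. A mood effect of CBT common to both tDCS arms cancels in the active-against-sham contrast, so a mood difference has to come from tDCS. Two routes are plausible.

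- **tDCS acts on mood directly.** The support is indirect: the Preliminary Studies section says that slow right prefrontal TMS "has anti-depressant effects as does fast (10 Hz) left prefrontal TMS". That concerns TMS and depression, not tDCS.
- **tDCS lowers pain, and less pain lifts mood.** The Brief Pain Inventory is described as a tool to "assess pain intensity and the impact of pain on general functioning, relationships and mood", and the Participants paragraph remarks that depression beginning after fibromyalgia is common in chronic pain. Mood is then a consequence of the outcome, and no separate mood effect of tDCS is needed.

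On either route the model subtracts part of the pain benefit that Hypothesis 1b is about. Attenuation is the likely direction but not a certain one. If active tDCS worsened mood, the benefit would be overstated. Unmeasured causes shared by mood and pain add further bias. Mood is not among the outcomes listed for analysis, so a difference between arms could go unnoticed.

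**Working it through.** **Timing.** Diary weeks: 2 + 6 + 4 = 12. After treatment starts: 6 + 4 = 10, and 10/12 = 83%. If six weekly sessions span five weeks, the share is 9/11 = 82%.

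**Formula.** Score mood as distress, with negative meaning less pain. Then

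adjusted effect = total effect − β × (arm difference in mood),

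where β is the mood coefficient in the pain model. The estimate shifts only if β and the arm difference are both non-zero.

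**Inputs.** From the documents: 72 patients, taken as 36 v 36 by tDCS. All else is assumed: total benefit 0.50 SD; 2 baseline and 6 treatment weekly scores; intraclass correlation 0.6; mood-pain correlation 0.5 between and 0.4 within patients; correlation 0.6 between patients' baseline and treatment levels; baseline pain in the model. The model is a simulated random-intercept model with 2000 replicates.

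**Direct effect on mood.** The simulated values match the formula with β about 0.4, for example 0.50 − 0.4 × 0.2 = 0.42.

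| Mood benefit (SD) | 0 | 0.1 | 0.2 | 0.35 | 0.5 |
|---|---|---|---|---|---|
| Formula, 0.50 − 0.4 × benefit | 0.50 | 0.46 | 0.42 | 0.36 | 0.30 |
| Simulated pain benefit | 0.498 | 0.460 | 0.420 | 0.365 | 0.300 |
| Power with time-varying mood | 0.896 | 0.854 | 0.780 | 0.650 | 0.472 |

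Without time-varying mood the estimate is 0.50 and power is 0.82 to 0.84. Adjustment therefore gains power up to a mood benefit of about 0.1 SD and loses it from about 0.2 SD. If mood worsened by 0.2 SD, the formula gives 0.50 + 0.4 × 0.2 = 0.58, an overstatement.

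**Pain drives mood, with no direct mood effect.** With standardised slope b, the retained share is about 1 − b².

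| Slope b | 0.3 | 0.45 | 0.6 |
|---|---|---|---|
| Formula, 0.50 × (1 − b²) | 0.455 | 0.399 | 0.320 |
| Simulated pain benefit | 0.460 | 0.406 | 0.322 |
| Share lost (simulated) | 8% | 19% | 36% |
| Power with time-varying mood | 0.786 | 0.734 | 0.601 |

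**No pain effect, but a shared cause of mood and pain.** The spurious harm is loading² × mood benefit: 0.4² × 0.2 = 0.03 SD and 0.6² × 0.5 = 0.18 SD.

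**Sensitivity.**
- Fully stable patient levels: 0.499/0.467/0.434/0.385/0.336 for the five mood benefits.
- No baseline covariate: 0.499/0.459/0.415/0.356/0.294.
- Person-mean centring does not remove the shift: for mood benefits of 0.2/0.35/0.5, 0.423/0.357/0.299 centred against 0.421/0.354/0.294 uncentred.
- A separate simulation with 10 post-start weeks, 2000 patients and intraclass correlation 0.5: with pain driving mood, 90%, 75% and 49% of the effect was retained at correlations 0.3, 0.5 and 0.7 (1 − r² gives 91%, 75% and 51%). With mood equal between arms, 97% to 100% was retained. Dropping time-varying mood, or using baseline mood only, gave estimates of 0.47 to 0.56 around the true 0.50.

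**The plan's power figure.** The stated power above 0.80 with 18 per group lacks alpha, a numeric effect size and correlations. It can be neither confirmed nor refuted, and this point does not depend on it.

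**The case against.** The harm is conditional, and no passage reports that tDCS changes mood. The closest evidence points the other way. The motor-cortex rTMS trial of 30 patients is summarised as having reduced pain and "improved quality of life in patients with fibromyalgia, without affecting mood or anxiety levels". The right-prefrontal rTMS trial of 26 found no depression benefit, though also no pain benefit. Entry criteria exclude HRDS above 18 and require BAI below 16, which leaves less room for mood to improve, so mood benefits of 0.35 to 0.5 SD may be high. The Background also says that emotional state contributes to pain, a possible reason to adjust. The Preliminary Studies argue that pain relief in a small rTMS series was probably not wholly due to treating depression, so a mood-independent question may be deliberate. If mood is unaffected, the planned model is unbiased and more powerful: 0.90 v 0.83 at 36 v 36. Hypothesis 1b compares CBT with and without tDCS, about 18 v 18 if four groups are equal, where the corresponding figures are 0.59 v 0.52.

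Much of this stands as a limit on likely size. It does not remove the point. The cited trials used another technique at other targets, so they do not show that mood will be equal here. If mood affects pain and tDCS affects mood, mood is a mediator; if pain affects mood, it is a consequence of the outcome. Neither belongs in the main model for a total effect. A mood-independent question would need to be stated, and it is not.

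Scope is also limited. Diaries end after the 4-week follow-up, so diary mood cannot adjust the 3- and 6-month assessments, and the functioning half of Hypothesis 1b is largely untouched.

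**Conclusion.** The concern holds as a conditional one and should be fixed before analysis. The only model described for pain, sleep and activity conditions on a variable recorded mostly after treatment starts, while Hypothesis 1b asks for the effect of adding tDCS. In the assumed settings at 36 v 36, a 0.50 SD pain benefit shrinks to 0.46 to 0.30 SD for direct mood benefits of 0.1 to 0.5 SD, and to 0.46 to 0.32 SD when pain drives mood. There is no bias if mood does not differ between arms, and the bias reverses if tDCS worsens mood. The actual size cannot be computed from the documents. Reading the mood term as concurrent diary mood is an inference, though a strong one. Confidence is medium.

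**What to change.** In the HLM for pain, sleep and activity, adjust only for values recorded before randomisation: baseline depression, anxiety and pain, and optionally mean diary mood over the 2-week baseline phase. Baseline-phase mood added nothing beyond baseline pain in the setting above (power 0.82 v 0.83). Keep the time-varying mood model as a labelled secondary or mediation analysis that states lag, centring and the assumption of no unmeasured confounding of mood and pain. Analyse daily mood as an outcome, so that any difference between arms is visible.

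This changes one clause and needs no new data. The cost is some power if treatment truly leaves mood alone:

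- With level stability 0.6: 0.90 to 0.83 at 36 v 36, and roughly 0.07 to 0.11 lost at 18 v 18.
- With fully stable levels: 0.995 to 0.994 at 36 v 36, and 0.885 to 0.873 at 18 v 18 (a loss of 0.012).

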MINIMALLY INVASIVE BRAIN STIMULATION AND PAIN: There is some evidence that electrical stimulation of the motor cortex can ameliorate pain²⁵⁻²⁸. The PFC is another studied target for pain relief, and may be specifically helpful in reducing the affective dimension of pain. Stimulation of the PFC increases thermal pain thresholds in healthy adults²⁴ and reduces neuropathic²⁹ and fibromyalgia pain^{23 30}. tDCS involves the application of low-amplitude electric current to the brain. A battery-powered current generator is attached to two sponge electrodes soaked in saline and held in place by a non-conducting montage. Sufficient current penetrates the brain and modifies transmembrane neuronal potential^{31, 32 33} influencing excitability and modulating the firing rate of neurons. Anodal tDCS applied over the human cortex increases excitability, while cathodal tDCS applied over the same area decreases it^{34 35 36, 37 38}. While tDCS appears to have direct effects on brain activity, structure, and neuronal organization, the effects are likely mediated by several factors, the most important of which may be the activity of the brain during stimulation. It appears that tDCS may be a brain stimulation tool that can be used to facilitate or inhibit endogenous cortical and subcortical processes, but not necessarily directly or independently engender large, directly observable behavioral changes unless strategically combined with specific brain activity patterns. This notion has already been embraced in the area of stroke rehabilitation wherein tDCS is combined with rehab therapy to produce significantly enhanced recovery effects.³⁹

COGNITIVE AND BEHAVIORAL ASPECTS OF PAIN PERCEPTION:

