COMBINED CBT and tDCS INTERVENTION EFFECTS ON PAIN PERCEPTION: To directly address the aims of the present proposal, in a recent preliminary pilot, the Investigators examined the effects of anodal versus cathodal tDCS over the left DLPFC in combination with a laboratory CBT intervention on thermal pain tolerance in 8 healthy volunteers. Participants underwent repeated heat tolerance testing using the Medoc Pathway system before, during and after the combined tDCS+CBT intervention. Participants were randomly assigned to receive anodal or cathodal tDCS delivered over the left DLPFC. For this preliminary pilot, participants all listened to a recording of a laboratory-version of a CBT intervention that focused on 3 distinct elements: 1) identification of catastrophizing language and replacement with more realistic and attenuated linguistic tags for thermal experiences. 2) identification and challenging of automatic negative self-effacing thoughts related to the tolerance task, and 3) a behavioral distraction strategy. Anodal tDCS applied to the left DLPFC during the CBT intervention was associated with a significant increase in thermal pain tolerance whereas cathodal stimulation appears to have blunted the analgesic benefit of the CBT intervention. Despite all subjects receiving the same CBT intervention, those that received simultaneous anodal stimulation of the left DLPFC found the CBT intervention significantly more helpful ($p<.05$) and found the strategies presented more useful in improving pain tolerance ($p<.05$) than those who received cathodal stimulation. These findings support the notion that engaging cognitive neural circuits that have been shown to play a role in the

down-regulation of pain experience and then exciting the circuits with tDCS might offer synergistic benefit.

D. RESEARCH DESIGN AND METHODS (including data analysis)

OVERVIEW: Pilot clinical trial-- Patients with FM will receive a brief course (6 sessions) of manualized CBT for pain (or education-only control) combined with anodal or sham tDCS over the left DLPFC

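### The design text conflicts on whether education-only arms exist, and the one stated model (active vs sham tDCS) has no term for the interaction it claims power for; with four groups it would understate Hypothesis 1b

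*Combined protocol and SAP*

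**What the plan says.** Section A sets the aim to "Determine the effects of CBT, anodal tDCS over left DLPFC, and combined CBT+tDCS on clinical pain and functioning". Hypothesis 1a is that "CBT alone will be associated with significant improvements in pain and functioning", with no comparator named. Hypothesis 1b is that "Anodal tDCS plus CBT will yield significant improvements in pain and functioning that exceed those of CBT alone".

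The Section D overview offers "manualized CBT for pain (or education-only control) combined with anodal or sham tDCS". That reads as two crossed factors and so four groups.

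Other passages read differently. tDCS Methods places stimulation, in all tDCS conditions, "during each of the 6 CBT sessions". Procedures has patients start CBT after baseline and describes only tDCS as randomised. Section E.3 says all participants might benefit from the CBT. The Clinical Pilot Trial paragraph fits either design. The number of arms and the allocation ratio are not stated.

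Data Analysis Plan and Power gives one model, a hierarchical linear model controlling for mood and for "baseline depression, anxiety and pain scores as a function of group (active vs sham tDCS"). The paragraph then claims:

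- power above .80 for a group main effect with as few as 18 per group, assuming medium effects and no interaction between tDCS and CBT;
- power above .90 for main and interaction effects if the interaction is large, which it says is expected.

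Other sections also point to synergy. Section B says tDCS may "not necessarily directly or independently engender large, directly observable behavioral changes unless strategically combined with specific brain activity patterns", and Section C concludes that pairing it with cognitive engagement "might offer synergistic benefit".

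**The concern.** A reader cannot tell how many arms there are, and the stated model does not match everything the plan wants from it on either reading.

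With four groups, a model containing only active versus sham tDCS averages the tDCS effect over CBT and education patients. Hypothesis 1b concerns the effect within CBT patients. The two differ whenever tDCS and CBT interact, which is what the plan expects. The CBT-versus-education comparison, which would give a controlled estimate of the CBT effect named in the Aim, is not specified either.

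With CBT for everyone, the model tests 1b properly, but the design contains no information on a tDCS-by-CBT interaction.

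Section E.4 says the findings will be used to evaluate the need for a larger multi-site trial, so the size of the 1b estimate matters even in a pilot. If the contrast is left open, it could also be chosen after the data are seen.

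**Working it through.** **Inputs.** N = 72 (Section D, Participants). 18 per group, described as a minimum, and effects given only as medium or large (Data Analysis Plan and Power). Not stated: alpha, sidedness, numeric effect sizes, SD, number of time points in the calculation, within-patient correlation, allocation. Assumed below: two-sided 0.05, SD 1, equal allocation, one endpoint, no dropout.

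**Number of groups.** 72/18 = 4, which fits the overview. Because 18 is a minimum, 72/2 = 36 per arm is also possible. The count supports four groups but does not settle it.

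**The plan's own power figure.** Taking medium as d = 0.5, a two-group comparison has power 0.31 with 18 per group and 0.55 with 36 per group. Averaging 2 to 6 repeated measures with correlation 0.3 to 0.7 (36 vs 36, f = 0.25) gives 0.62 to 0.90. A group-by-time test with two groups of 18, two times, f = 0.25 and correlation 0.5 gives 0.83. The stated figure above .80 can be neither confirmed nor refuted, and this point does not rest on it.

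**Four equal groups.** Let D_C be active minus sham within CBT (the 1b contrast), D_E the same within education, and I = D_C − D_E. A model with only the tDCS factor estimates

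(D_C + D_E)/2 = D_C − I/2.

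In 2,000 simulated trials with D_E = 0.5 and I = 0.8, the means were 1.295 for 1b and 0.898 for the one-factor term. The algebra gives 1.3 and 1.3 − 0.4 = 0.9. If a proportion p of each tDCS arm received CBT, the term would be D_C − (1 − p)I, so the factor of one half depends on p = 1/2.

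Standard errors in SD units, unadjusted: pooled term √(2/36) = 0.24; 1b contrast √(2/18) = 0.33; interaction √(4/18) = 0.47. Power below is noncentral t with 68 df; the pooled column has CBT and the interaction in the model.

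| D_E | I | 1b = D_E + I | Pooled = D_E + I/2 | Power, pooled | Power, 1b contrast |
|---|---|---|---|---|---|
| 0 | 0.8 | 0.80 | 0.40 | 0.39 | 0.66 |
| 0.25 | 0.5 | 0.75 | 0.50 | 0.55 | 0.60 |
| 0.5 | 0.5 | 1.00 | 0.75 | 0.88 | 0.84 |
| 0.5 | 0 | 0.50 | 0.50 | 0.55 | 0.32 |

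With CBT omitted, as the model is written, and an assumed CBT effect of 0.5 SD, the pooled powers become 0.30, 0.49, 0.85 and 0.53.

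**Interaction power, 18 per cell.** 0.39 at 0.8 SD, 0.92 at 1.6 SD, and 0.90 at about 1.55 SD. Baseline adjustment at an assumed correlation of 0.7 lowers that threshold to 1.55 × √(1 − 0.49) = 1.11 SD. Repeated measures could lower it further.

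**CBT for all.** With the CBT indicator equal to 1 for everyone, the columns for intercept, tDCS, CBT and tDCS × CBT have rank 2 of 4. The tDCS term is exactly the 1b contrast (36 vs 36, SE 0.24). The CBT effect and the interaction cannot be estimated.

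**The case against.** The strongest reply is that silence is being read as exclusion. The plan is one paragraph, the wording about group may be shorthand, and a paragraph that expects to detect an interaction implies that one will be fitted. This stands in part: it is not established that 1b will be estimated wrongly. But the paragraph defines the group factor explicitly and names no CBT or interaction term, so the gap is in the text.

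Second, only the overview mentions education; the Aim, the interaction wording and 4 × 18 = 72 are indirect support. If everyone receives CBT, there is no biased 1b. This stands.

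Third, Hypothesis 1a as worded can be met by within-arm change. That is so, although such change is uncontrolled.

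Three stronger readings are tempting and not supported:

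- A reader might infer that the stated factor suits neither design. With CBT for all it is exactly the 1b contrast.
- A reader might halve the 1.55 SD threshold and treat 0.78 SD as the least possible understatement. That holds only for one unadjusted endpoint, whereas the plan adjusts for baseline pain and collects daily diaries.
- A reader might infer that pooling generally loses power. In the table it has more power when the interaction is absent or no larger than the stand-alone effect; its fault is that it estimates a different quantity.

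**Conclusion.** Wrong as written. The design passages conflict, and the plan claims power for an interaction that its stated model has no term for under either reading.

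With four equal groups and literal use of the one-factor model, the tDCS term understates 1b by half of any positive interaction: 0.40 against 0.80 SD in the assumed case where tDCS works only with CBT. The two agree only when there is no interaction, which the plan uses as its conservative assumption and does not expect. Confidence that 1b would be biased is moderate, because it depends on education arms existing, on roughly equal allocation and on the model being applied as written. The effect sizes are assumptions; the algebra needs none of them.

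With CBT for all, 1b is tested correctly, 1a is an uncontrolled within-group change, and the interaction power claim cannot stand.

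Section E.4 should not be read as saying that these results will by themselves settle whether a larger trial goes ahead; it says only that they will inform that evaluation.

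**What to change.** Reconcile the Section D overview with tDCS Methods, Procedures and Section E.3, and state the number of arms and the allocation.

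**If education arms exist:**

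- Fit tDCS, CBT/education, their interaction, and each by time, keeping the baseline covariates.
- Pre-specify 1b as CBT plus active against CBT plus sham in change from baseline.
- Report the CBT-versus-education contrast as the controlled CBT estimate, with within-arm change as the literal 1a.
- Give the numeric effect size, metric and assumptions behind the interaction power claim.

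**If all patients receive CBT:** keep active versus sham for 1b, describe 1a as uncontrolled, and delete the interaction power claim.

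The cost is a few sentences and no new data. With four groups, the direct 1b contrast is less precise (SE 0.33 against 0.24 SD, unadjusted). If there is in fact no interaction, it gives up power (0.32 against 0.55 at 0.5 SD). The pooled tDCS main effect can be reported alongside. With CBT for all, 1b keeps SE 0.24 SD, and the loss is the interaction claim and any controlled test of 1a.
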